Average HbA1c among youth in the US in 2016 was 8.8%, considerably above the standard clinical target of < 7.5%, and had worsened significantly since 2011. The emphasis of the last two decades on flexible patterns of dietary intake for youth with T1D has clearly not corresponded with adequate glycemic control, despite increased use of insulin pumps and continuous glucose monitoring (CGM) in that time period. There are major gaps in knowledge about what interventions might achieve improved glycemic control, and what approach to patterns of dietary intake might be beneficial. Some T1D clinical practice guidelines explicitly recommend use of planned eating patterns. Additionally, consensus in some pediatric diabetes clinics with excellent glycemic control suggests that planned eating is a key element in successful diabetes management. Remarkably, there are no clinical trial data on the effectiveness of this strategy for glycemic control, nor data on the acceptability of and adherence to this strategy among youth with T1D. **Thus, our overarching goal is to rigorously test the effectiveness of individualized, planned eating patterns to improve glycemic levels so as to inform T1D clinical practice guidelines.** We have completed several preliminary studies that support the likely acceptability and effectiveness of an individualized structured eating plan intervention we called “MyPlan”, that includes collaborative development of the individualized planned eating plan to spread intake of carbohydrate and calories over the day. **Here we propose a pilot single arm 6-month clinical trial to inform a future, fully powered pragmatic trial that tests the addition of individualized structured eating plans to ongoing diabetes care in clinical settings.** Our Specific Aims are: **Aim 1. Assess acceptability and adherence (primary outcomes) to a 6-month individualized planned eating intervention (“MyPlan”) among 40-50 youth with T1D.** We will recruit adolescents, age 12-17 years, with T1D of at least 1-year duration and with HbA1c between 7.5 % and 11% (total n=50 recruited to ensure n=40 active participants across two clinical sites) to participate in a 6-month MyPlan intervention, which will guide participants in setting behavioral goals in relation to five tenets that comprise a structured eating pattern. **Aim 2. Compare glycemic control among adolescents with T1D at baseline and at the end of the 6-month MyPlan intervention.** Measures of glycemic control will include % time in range (TIR) based on continuous glucose monitoring (primary outcome) and HbA1c (secondary outcome).

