Participant guardians and participants will have the opportunity to provide informed consent and assent, respectively, following the recruitment processes detailed above. For guardians and participants who agree to participate and schedule a baseline visit, at the time of the visit, study staff will review the full study consent in detail before standardized data collection begins. Guardians and participants will be given as much time as needed to review the consent and assent forms and ask any questions prior to signing it. They will be informed that participation in the study is voluntary and that they are free to withdraw their consent and discontinue participation in this research study at any time by contacting the primary investigators or study staff.

Following assent, participants may be involuntarily withdrawn from the study per the investigator's discretion if they develop a serious condition that would render participation unwise, including clinical diagnoses of serious physical or psychiatric conditions. The study physicians ([name], [name]) will review this information and make a determination about withdrawal from the study. Females who become pregnant will also be withdrawn from study participation.

If a participant chooses to withdraw or is withdrawn from the study, they will be asked the reason for withdrawal, which will be recorded in a withdrawal form in REDcap by study staff.

8. Standardized Measurements

Measurement	2-week run-in Baseline Data Collection Visit 1 Insert CGM	Week 3 Baseline Data Collection* First Session	Week 4-10 7 Weekly Sessions	Week 12-22 6 Bi-weekly Sessions	Week 22 Insert CGM	Week 24 Last Session take-off CGM	Week 26 Endline Data Collection Visit 2 return CGM
Adherence							
Mobile Phone MyFitnessPal Logs	X	X	X	X	X	X	
24-Hour Diet and Physical Activity Recalls	X				X		
Acceptability							
MyPlan Acceptability Assessment (Parent, Participant)				X	X	X	X
MyPlan Adjustment Form			X	X	X	X	X
MyPlan post-hoc qualitative evaluation							
Psychosocial and Behavioral Factors							
Baseline Lifestyle Questionnaire	X						
Diabetes Self-Management Support	X						X
Food Frequency Questionnaire	X						X
Diabetes Eating Problem Survey	X						X
Hypoglycemia Fear Survey	X						X
Knowledge Survey	X						X
Self-Efficacy Survey*		X*					X
Motivation*		X*					X
Problem Solving Skills*		X*					X
Glycemic Control							
Continuous glucose monitoring	X				X		X

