Alignment of participant behavior to the prescribed eating behavior pattern will be objectively assessed via two unannounced 24-hour dietary recalls (1 weekday, 1 weekend per week) collected during the 0-2 week and 22-24 week CGM wear time of the MyPlan study. Adherence metrics (weekday and weekend) will include proportion of participants who followed each eating behavior target, proportion of participants who met 0-5 eating behavior targets, and average number of targets met

In exploratory analyses, participant logs and 24-hr recalls will also enable identification of which snacks/meals are most often missed, which snacks/meals deviate the most from time or carbohydrate distribution targets as specified in the planned eating plan, as well as which aspects of regular eating pose the biggest challenges to adherence. These metrics will help with targeting counseling and focusing goal-setting, as well as areas to focus the design of future trials.

Eating behavior pattern acceptability

Although acceptability of the individualized planned eating plan will be ascertained every week after the plan is introduced, acceptability will be reviewed formally at 3 months, and again at the conclusion of the intervention period. Participants and their parent/guardians will fill out an acceptability assessment that we have used in previous studies.^{101 17} We will calculate separate composite acceptability scores (5 highly acceptable, 20 highly unacceptable, >10 unacceptable) from ordinal responses to statements from an 5-item instrument designed to capture ease of eating pattern

adoption, satisfaction, food enjoyment, sustainability, and ease of blood sugar management. As part of the post-hoc qualitative evaluation of the intervention, we will conduct short semi-structured qualitative exit interviews with teenager and parent participants and project staff to ascertain barriers and facilitators to following the eating strategy, likes and dislikes, recommendations for modifications, likelihood of recommending the strategy to others, and the eating behavior target participants found most difficult to follow, alongside other feedback related to intervention design, materials, and implementation.

8b. Secondary Outcomes

HbA1c

At baseline and 26 weeks, HbA1c will be measured using point-of-care testing.

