The schedule of intervention sessions, measurements, and questionnaires is depicted in **Figure 3** below.

Figure 3. MyPlan Study Schedule of Intervention Sessions, Measurements, Questionnaires

Participant Timeline	In-Person Visits	Remote Video Sessions with Dietician	Remote Food and Exercise Measurements	Remote Questionnaires
Week 1	HbA1c, Height, Weight Insert CGM	1 session	MyFitnessPal logs 1 weekday 1 weekend 24-hour recall	Most Questionnaires
Week 3-10	Mail back CGM (Week 3)	8 sessions (every week)	MyFitnessPal logs	Eating Plan Questionnaires (Week 3)
Week 12-24	Receive CGM (Week 21) Insert CGM (Week 22)	7 sessions (every other week)	MyFitnessPal logs 1 weekday 1 weekend 24-hour recall (Week 22)	Acceptability Questionnaire (Week 14)
Week 26	HbA1c, Height, Weight Return CGM			All Questionnaires

In-person visits

Participants and their parents/guardians will attend two in-person measurement visits at baseline and end (26 weeks) of the intervention. HbA1c, height, and weight will be collected at these time points. Although participants will be sent questionnaires electronically ahead of the measurement visit, participants will finish any outstanding questionnaires in person to ensure data completeness. At the baseline visit, after consent/assent is completed, the participants will be given the blinded CGM, and explained how to insert it independently. They will insert it at the Baseline session with the study dietitian. Participants will be provided a pre-paid envelope to send back the CGM after 2 weeks of wear time. Participants will receive another CGM in the mail at 22 weeks, which they will insert independently to avoid the burden of another in-person visit. They will receive virtual insertion assistance from the study dietitian at the 22 week session. They will return the CGM at the 26 week in-person visit. Two 24-hour dietary and physical activity recalls will be collected during the 2 week CGM wear time at both time points.

Counseling and online intervention sessions

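### Dyads who withdraw between week 3 and the first five-item acceptability assessment (about weeks 12–14) have no planned score on a primary outcome

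*Combined protocol and SAP*

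**What the plan says.** The first aim in Section 1 reads "Assess acceptability and adherence (primary outcomes", and the synopsis also lists acceptability among the primary measures. Section 3 intends the five-item questionnaire for every participant. Section 8a sums the items to a composite, separately for youth and guardian, with anchors and cut-off "5 highly acceptable, 20 highly unacceptable, >10 unacceptable".

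On timing, Section 8a states that "acceptability of the individualized planned eating plan will be ascertained every week after the plan is introduced, acceptability will be reviewed formally at 3 months", with a second formal review when the intervention ends. In the Section 8 schedule, the row "MyPlan Acceptability Assessment (Parent, Participant" has its first mark in the week 12–22 column and none in the week 3 or week 4–10 columns. Figure 3 in Section 9 lists "Acceptability Questionnaire (Week 14". Section 8c (MyFitnessPal logs) places delivery of the eating plan in week 3.

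On leaving, Section 6 tells families they are "free to withdraw their consent and discontinue participation in this research study at any time". When a participant withdraws or is withdrawn, "they will be asked the reason for withdrawal, which will be recorded in a withdrawal form in REDcap by study staff". No other data collection at exit is described. Section 11 reports acceptability continuously and categorically, but gives no time point, denominator or rule for missing scores.

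**The concern.** Leaving early may be one of the clearer signs that a youth or guardian finds the plan hard to live with. About 9 to 11 weeks on the plan pass before the five items are first given (week 3 to weeks 12–14), and a dyad that withdraws in that time is never asked them. The mean score and the percentage acceptable would then describe only those who stayed long enough to be asked.

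The trial is meant to inform whether planned eating goes into a fully powered study. An acceptability figure that leaves out early leavers, without saying so, could make the plan look easier to adopt than it was. The five-item answers of these dyads cannot be reconstructed afterwards.

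**Working it through.** **Inputs from the documents**
- Enrolment of 50 dyads (33 and 17), planned retention 80%, at least 40 completers (26 and 14): Section 5.
- Retention of 93% in the earlier 18-month trial: Section 5.
- Plan introduced in week 3; first five-item assessment in the week 12–22 column or at week 14: Sections 8, 8c and 9.
- Composite runs from 5 (best) to 20 (worst), with scores above 10 unacceptable: Section 8a.

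**The plan's own figure.** 50 × 0.80 = 40 completers, so 10 losses. By site, 33 × 0.80 = 26.4 and 17 × 0.80 = 13.6, which round to 26 + 14 = 40. The figure reproduces.

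**Assumptions, not in the documents.** 80% of scored dyads find the plan acceptable. A share f of the losses falls after week 3 but before the first assessment, and none in the run-in. Losses after the first assessment keep their midpoint score.

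**Formula.** Let e be the number of early leavers, p the proportion acceptable among those scored, and q the proportion of early leavers who would have scored the plan acceptable.

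Proportion over all 50 = [p × (50 − e) + q × e] / 50

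Overstatement = p minus this = (e/50) × (p − q)

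**80% retention (10 losses), p = 0.80, q = 0**

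| f | e | scored | over all 50 | overstatement |
|---|---|---|---|---|
| 25% | 2.5 | 47.5 | 38/50 = 76% | 4 points |
| 50% | 5 | 45 | 36/50 = 72% | 8 points |
| 75% | 7.5 | 42.5 | 34/50 = 68% | 12 points |
| 100% | 10 | 40 | 32/50 = 64% | 16 points |

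**93% retention (3.5 losses), p = 0.80, q = 0.** With f = 25%, 0.80 × 49.125/50 = 78.6%. With f = 100%, 0.80 × 46.5/50 = 74.4%.

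**Opposite extreme.** If all 10 losses are early and every one would have scored the plan acceptable (q = 1), the figure is (32 + 10)/50 = 84%. The completers' 80% would then understate acceptability by 4 points.

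**Precision for scale.** Exact 95% intervals are 64–91% for 32/40 and 49–77% for 32/50.

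**Mean score (assumed values).** With a mean of 9 in 40 completers and 15 in 10 early leavers, (40 × 9 + 10 × 15)/50 = 10.2, which is above the protocol's cut-off of 10, whereas 9 is below it.

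**Whether other planned data supply the score.** The weekly ascertainment in Section 8a has no instrument or score attached, and the schedule shows no weekly use of the five items. The adjustment form (from weeks 4–10), logs, goals and attendance do not give the 5–20 composite. The qualitative evaluation in Section 11 takes a sub-sample chosen by change in HbA1c or TIR from baseline to endline, which an early leaver does not have.

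**The case against.** A reader might infer four stronger points that the documents do not support.

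- **That stopping the plan means leaving the study.** Section 6 covers only choosing to withdraw or being withdrawn. Elsewhere the protocol expects youth who struggle to remain: adherence is reported down to zero targets met, those who stop logging get dietitian outreach and simpler logs, and the plan is revised at midpoint. A youth who gives up the plan without withdrawing is still due the later assessments. The protocol is silent on this group; it does not exclude them.
- **That nobody who quits is ever scored.** Anyone leaving after weeks 12–14 should already have a midpoint score. What is undefined is whether it counts.
- **That acceptability is overstated by 12 to 16 points.** That needs all 10 losses to be early and no more than 2 of the 10 to be favourable: (32 + 2)/50 = 68% and 32/50 = 64%. The documents give neither the timing nor the reasons for losses. Illness and pregnancy also lead to withdrawal, so leaving is not the same as disliking the plan.
- **That analysis can do nothing about it.** The recorded reason can identify those who left over the plan, and they can be counted as unacceptable or bounded, as above. This protects the inference in part; it does not produce the missing scores.

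Two further points are fair. Acceptability is not the only basis for a later trial: adherence and TIR are also primary, and no go/no-go threshold is set. Excluding unwilling youth at entry does not add to the bias, because the synopsis says the same criteria are planned for the full trial.

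What stands after all this is the unscored interval, the lack of an exit assessment, and the absence of a rule on time point and denominator.

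**Conclusion.** The point holds for dyads who withdraw after week 3 and before the first five-item assessment. They have no planned composite score on a primary outcome that Section 3 intends to collect from everyone. For later leavers, the plan leaves open whether the midpoint score is used.

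The likely direction is towards overstating acceptability, but this is not certain: it depends on early leavers being less favourable than those scored. At the planned 80% retention, the overstatement ranges from 4 to 16 points as the early share of losses goes from 25% to 100% with all early leavers unfavourable. It is about 1 to 6 points at 93% retention, and it reverses to a 4-point understatement if all 10 leavers are early and favourable. The 80% rate, the timing of losses and the leavers' views are assumptions. This is a cheap improvement to make, not a flaw that undermines the trial.

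**What to change.** 1. **Section 6:** offer the existing five-item assessment, youth and guardian versions, with the REDCap withdrawal form to anyone who leaves after the plan is introduced in week 3.
2. **Section 11:** report acceptability out of all dyads who started the plan. For leavers, use the last available score (exit or midpoint) and label it as such. Add a sensitivity analysis that counts unscored leavers as unacceptable.
3. **Withdrawal form:** the protocol does not address youth who stop the plan or sessions but are willing to be measured. Record this separately from withdrawal from all data collection, and invite that group to the measurements already scheduled at weeks 22–24 and week 26.

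The cost is five existing items on an existing form, plus protocol and consent wording. There are three drawbacks. Some leavers will decline. Exit scores come from different time points than endline scores, so they should be shown separately as well as combined. The reported acceptability may also look less favourable.

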Aim 1. Assess acceptability and adherence to a 6-month individualized planned eating strategy (“MyPlan”) among 40 youth with T1D. We will recruit adolescents, age 12-17 years, with T1D of at least 1-year duration and with HbA1c 7.5 % and 11%. Coordinated at the University of North Carolina at Chapel Hill (UNC), we will recruit 17 participants at UNC and 33 participants at Cincinnati Children’s Hospital Medical Center diabetes clinic (total n=50 recruited to ensure approximately n=40 completers) to participate in a 26 week MyPlan intervention, which will guide participants in setting behavioral goals in relation to five behavioral targets that comprise a eating behavior pattern (“MyPlan”) developed based on clinical expertise and international consensus guidelines: 1) 3-4 meals and 1-2 optional snacks; 2) spacing eating occasions throughout the day; 3) spacing carbohydrates across the day; 4) no post-dinner snacking; and 5) eating within a short period of waking.

- **To assess acceptability** we will use a previously developed five-item questionnaire for diet acceptability (all participants) as well as a post-study qualitative evaluation (sub-sample of participants):
 - Satisfaction, perceived ability to stay on the plan, enjoyment of the plan, ease of staying on the plan, how the participant feels on the plan and ability to manage blood sugar on the plan.
 - Perceived pros and cons of the plan, and other acceptability related themes that emerge from answers to questionnaire free response items and qualitative evaluation questions
- **To assess adherence** we will use 24-hour dietary recalls and MyFitnessPal logs to calculate:
 - Weekday and weekend adherence (categorically and continuously specified) to five behavioral targets that define the MyPlan pattern will be calculated
 - Consistency will be defined as the extent to which youth performance on the adherence metrics differs between the dietary recall/log days.

Aim 2. Compare glycemic control among adolescents with T1D at baseline and at the end of the 6 month MyPlan intervention.

- **To assess glycemic control we will use % time in range (TIR) and HbA1c.** The primary glycemic control outcome will be pre-post within-person change in % TIR measured by CGM. With 80% power, we will be able to detect an approximate change in TIR of 6.8%, equivalent to a change in HbA1c of about

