The two step-recruitment process is a pre-emptive retention strategy because it ensures parents and adolescents have an in-depth understanding of study expectations and helps them reflect on barriers to participation before signing on to the study. Further, staff will remotely monitor participation (i.e., adherence to MyFitnessPal logs) on a weekly basis to actively and pre-emptively troubleshoot engagement issues. Additionally, we will incorporate successful retention strategies from previous research in this study population (e.g., offering flexible visit options, incentives [up to \$200] based on questionnaire/measurement completion and intervention participation, reminder texts/e-mails, cards and phone calls, easy parking instructions). Using similar strategies in the 18-month FLEX trial, our retention was 93%.⁹¹ We expect the same success for MyPlan because it has approximately identical inclusion criteria as FLEX, is significantly shorter in length, and only requires two in-person measurements visits (counseling sessions and questionnaires will be completed online) –all of which make the study lower burden and more convenient for participants than the FLEX study. We also anticipate that the point-based incentive system that rewards participants We will recruit 50 youth-guardian dyads (33 at CCHMC, 17 at UNC). We

conservatively plan for 80% retention, resulting in at least 40 completers (26 at CCHMC, 14 at UNC).

Participant Recruitment: Ohio: The recruitment goal for Ohio is 33 participant/guardian dyads. Participants will be recruited from the Cincinnati Children's Hospital and Medical Center pediatric endocrinology clinic, located on the campus adjacent to University of Cincinnati. Clinics outside of Cincinnati Children's Hospital and Medical Center may also be sources of potential participants, who will either be identified through Facebook groups or MyPlan staff networks.

Participant Recruitment: University of North Carolina: The recruitment goal for University of North Carolina at Chapel Hill is 17 participant/guardian dyads. Participants will be recruited from the University of North Carolina medical system. Clinics outside of University of North Carolina medical system may also be sources of potential participants, who will either be identified through Facebook groups or MyPlan staff networks.

6. Consent, Assent, Withdrawals

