Power analyses are based on matched-pairs t-tests and a conservative estimate of 40 participants (alpha level of 0.05). Drawing from our previous study with a similar population to estimate the within-subject correlation, we have 80% power to detect an improvement in TIR of 10%.⁹⁴ In this previous study, the average TIR was 34.7% (SD=13.6), so this would correspond to an increase to an average of 42.5% TIR. The detectable effects are large, which is appropriate in this study that aims to assess preliminary effectiveness and acceptability to inform the design of a future fully-powered RCT of longer duration.

Outcome evaluation

Aim 1. Assess acceptability and adherence to a 6-month individualized planned eating intervention (“MyPlan”) among 40 youth with T1D.

1) Adherence:

We will calculate and report continuous and categorical overall adherence to the eating behavior pattern and adherence specific to each of the five eating behavior targets that make up the pattern (i.e. mean number of eating behavior targets met, proportion of participants who met each type of target, proportion of individuals who met 0, 1, 2, 3, 4, or 5 targets). Further exploratory modeling will be conducted to identify the contributions that adherence to each of the five individual behavioral targets make to overall adherence scores, as well as the relative magnitude of associations between adherence to each of the five individual behavioral targets and glycemic measures.

Acceptability:

- We will calculate continuous and categorical participant and guardian acceptability of the eating behavior pattern. Additional analyses include combined composite scores, exploratory modeling of demographic, clinical, and psychosocial predictors of acceptability will be conducted to inform both recruitment and targeted counseling strategies in future trials. We will assess acceptability related themes that emerge from answers to questionnaire free response items and questions posed as part of the qualitative post-hoc analysis of the intervention.

Aim 2. Compare glycemic control among adolescents with T1D at baseline and at the end of the 6month MyPlan intervention.

2) Effect on glycemic control:

We will compare continuous difference in TIR under the eating behavior pattern (22-24 weeks) vs. usual diet (0-2 weeks). We hypothesize that a) $TIR_{MyPlan \text{ eating behavior pattern}} > TIR_{\text{usual diet}}$

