- a) Matched-pairs t-tests will compare average TIR at 22-24 weeks vs. 0-2 weeks (overall and stratified by day/night)

- b) Linear regression modeling will examine whether change in overall degree of adherence (comparing the two 24-hour recall days at 22-24 weeks and two 24-hour recall days during 0-2 weeks) is associated with average change in 14 day TIR at endline vs. baseline
- c) Linear regression modeling will examine whether change in overall degree of adherence (comparing the two 24-hour recall days at 22-24 weeks and two 24-hour recall days at during 0-2 weeks) is associated with change in TIR using the two days of CGM data at 22-24 weeks and 0-2 weeks that are matched to the two 24-hour recalls collected at those time points.
- d) Exploratory linear regression modeling will assess whether the differences in TIR observed in models (a) (b) and (c) above persist after adjustment for self-management technology use (i.e., insulin pump vs. multiple daily injections, routine personal CGM use), physical activity, and other key clinical and demographic factors (i.e., age, sex, insurance status, parental education or other measure of socioeconomic status). Before including any of these factors in the model, we will examine their distributions as well as their bivariate associations with TIR to assess the magnitude, precision, and functional form of the relationship. An *a priori* ranking of the relative importance of these factors based on theory and existing literature will also inform the sequence with which we add them to the model. Changes in magnitude and precision of beta coefficients when different combinations of the variables are included in the model will also be considered in selection of the fully adjusted model.
- e) As part of the post-hoc qualitative evaluation of the MyPlan pilot intervention (detailed in a subsequent section), we will more deeply explore potential reasons underlying why the MyPlan eating behavior strategy may have improved or failed to improve participants' glycemic management to identify intervention levers for future studies. We will probe participants and staff about their perceived effectiveness of the strategy and reasons for this self-reported effectiveness via interviews and focus groups with project staff and a sub-sample of participants.

Process evaluation

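### The change in time in range detectable with 80% power is given as 10%, as a rise of 7.8 points and as 6.8%, and the inputs needed to check any of them are not stated

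*Combined protocol and SAP*

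**What the plan says.** Section 3 (Aim 2) defines the endpoint: "The primary glycemic control outcome will be pre-post within-person change in % TIR measured by CGM". The same paragraph states: "With 80% power, we will be able to detect an approximate change in TIR of 6.8"%, and equates this with a change in HbA1c of about 0.52%. That sentence carries no sample size or alpha, although Aim 1 in the same section expects about 40 completers.

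Section 11 (Statistical power) rests on matched-pairs t-tests, an alpha of 0.05 and "a conservative estimate of 40 participants". It says that the within-subject correlation was estimated from a previous study in a similar population, and that "we have 80% power to detect an improvement in TIR of 10"%. The previous study's mean TIR is given as 34.7% (SD 13.6), "so this would correspond to an increase to an average of 42.5% TIR".

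The planned analysis, in Section 11 under Aim 2, item (a), is: "Matched-pairs t-tests will compare average TIR at 22-24 weeks vs. 0-2 weeks". The hypothesis above it is directional (TIR higher under the eating plan than under usual diet), but no one- or two-sided test is named there or in the power paragraph.

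The figure of 40 comes from Section 5, where the investigators "conservatively plan for 80% retention, resulting in at least 40 completers" out of 50 recruited.

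**The concern.** There are two separate problems.

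- **Within Section 11:** a 10% improvement and a rise from 34.7% to 42.5% are presented as the same quantity, and they are not.
- **Between sections:** Section 3 claims the same power for 6.8%, and nothing in the documents reconciles this with either figure in Section 11.

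TIR change is the primary glycemic outcome, and the power paragraph says that the study is to inform a fully powered randomized trial. As written, a reader cannot tell which change the study can detect with 80% power. None of the figures can be checked, because the correlation is attributed to an earlier study but not reported. The HbA1c equivalent is attached only to the smallest figure.

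**Working it through.** **Inputs from the documents.** Section 11: paired t-test, n=40, alpha 0.05, power 80%, previous-study mean 34.7 and SD 13.6, end value 42.5, improvement 10%. Section 3: change 6.8%.

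**Not given, so assumed.** Two-sided test, and SD 13.6 at both times. The correlation r is varied.

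**Step 1: the end value (no assumptions needed).**

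- 42.5 - 34.7 = 7.8 points; 7.8 / 34.7 = 22.5% relative.
- 10 points: 34.7 + 10 = 44.7.
- 10% relative: 34.7 × 1.10 = 38.2, a gain of 3.47 points.
- Section 3's figure: 34.7 + 6.8 = 41.5.

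None of the three alternatives gives 42.5.

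**Step 2: trying to reproduce each figure.** The detectable change is δ = d × SD_change, with SD_change = 13.6 × √(2(1 - r)). Here d is the standardized change that gives 80% power under the noncentral t distribution with 39 degrees of freedom and noncentrality d√40. For a two-sided alpha of 0.05, d = 0.4543. Solving for the correlation gives r = 1 - (δ/d)² / (2 × 13.6²). For 10 points: 10 / 0.4543 = 22.01, and r = 1 - 484.4 / 369.9 = -0.31.

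| Stated change | Implied SD of change | Implied r |
|---|---|---|
| 6.8 points | 14.97 | 0.39 |
| 7.8 points | 17.17 | 0.20 |
| 10 points | 22.01 | -0.31 |
| 10% relative (3.47 points) | 7.64 | 0.84 |

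In the other direction:

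| r | 0 | 0.2 | 0.39 | 0.5 | 0.8 |
|---|---|---|---|---|---|
| Detectable change (points) | 8.74 | 7.81 | 6.82 | 6.18 | 3.91 |

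With equal SDs, 10 points exceeds the 80% value at every non-negative correlation.

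**Step 3: can other settings reconcile the figures?**

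- *One-sided test or n=50.* d becomes 0.4002 (n=40, one-sided) or 0.4042 (n=50, two-sided). At r = 0.20, SD_change is 17.20, and the detectable change is 7.81 (n=40, two-sided), 6.88 (n=40, one-sided) or 6.95 (n=50, two-sided). So 6.8 and 7.8 could come from nearly the same correlation under different settings. Ten points would then need r of about -0.69 (one-sided) or -0.66 (n=50).
- *Larger endline SD s.* Solving 13.6² + s² - 2 × r × 13.6 × s = 22.01² gives s of about 17.3 at r=0, 20.2 at r=0.2 and 23.4 at r=0.39. The documents give no such value.
- *13.6 read as the SD of change.* The detectable change is 0.4543 × 13.6 = 6.18 two-sided, or 0.4002 × 13.6 = 5.44 one-sided. This matches none of the stated figures.

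**Step 4: what the choice means for power (n=40, two-sided).**

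| If the true 80% figure is | Power for 6.8 | Power for 7.8 |
|---|---|---|
| 6.8 points | 0.80 | 0.895 |
| 7.8 points | 0.685 | 0.80 |
| 10 points | 0.478 | 0.589 |

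With SD 13.6 at both times, power for 10 points is 0.894 at r=0, 0.948 at r=0.2 and 0.995 at r=0.5.

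**The case against.** The strongest defence concerns Section 3. Its figure is described as approximate and carries no n or alpha. Step 3 shows that a correlation near 0.20 gives 7.8 points two-sided at n=40, and about 6.9 to 7.0 one-sided or at n=50. The directional hypothesis in Section 11 makes a one-sided calculation conceivable. So 6.8 and 7.8 need not rest on different data. That stands, but the plan states none of it.

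A second defence reads 10% as relative, which a correlation of 0.84 would support. That reading ends at 38.2%, so the same sentence's 42.5% contradicts it. A gain of 3.47 points also sits badly with the paragraph's own description of the detectable effects as large. Nor can any correlation, sidedness or sample size make 10% of either kind equal a rise from 34.7 to 42.5.

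Third, this is a single-arm feasibility pilot. Acceptability and adherence are its Aim 1 outcomes, its 40 completers follow from 80% retention of 50 and not from a TIR target, and no go/no-go rule uses the detectable change. This limits the consequence: the sample size and analysis are not undermined. It does not make the power statement correct.

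**Conclusion.** The power statement is wrong as written and should be corrected. The contradiction in Section 11 rests on subtraction alone: 10% is equated with a 7.8-point rise. Section 3 adds an unreconciled 6.8%.

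The implied correlations (0.39, 0.20 and -0.31 for 6.8, 7.8 and 10 points) assume n=40, two-sided testing, SD 13.6 at both times, and 13.6 being the between-participant SD. Under those assumptions 10 points is the least plausible of the three as an 80% figure. It would need a negative correlation, or an endline SD of at least about 17.3 if the correlation is not negative. The documents do not allow a choice between 6.8 and 7.8.

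The finding does not show that 40 participants are too few. With equal SDs and two-sided testing, power for 10 points is at least 89% at any non-negative correlation.

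**What to change.** Recompute the detectable change from the previous study's within-subject correlation or SD of change. State that input, the sidedness and n. Give one detectable change, in percentage points, with its matching endline mean and HbA1c equivalent, in both Section 3 (Aim 2) and Section 11 (Statistical power). Remove any figure that the recalculation does not support. Name the sidedness in the analysis item as well.

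For illustration only (n=40, two-sided, SD 13.6 at both times):

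| r | Detectable change (points) | Endline mean |
|---|---|---|
| 0.20 | 7.8 | 42.5% |
| 0.39 | 6.8 | 41.5% |
| 0.50 | 6.2 | 40.9% |

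The cost is one recalculation from data that the sponsor says it has already used, and wording in two sections. No participants are added and the planned test does not change. The supported figure may turn out less favourable than 6.8.
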